### 3.4.4 Exploratory Endpoints

#### 3.4.4.1 [REDACTED]

[REDACTED]

[REDACTED]

[REDACTED]

[REDACTED]

[REDACTED]

#### 3.4.4.2 [REDACTED]

[REDACTED]

[REDACTED]

[REDACTED]

[REDACTED]

[REDACTED]

[REDACTED]

#### 3.4.4.3 [REDACTED]

#### 3.4.4.4 [REDACTED]

[REDACTED]

[REDACTED]

[REDACTED]

[REDACTED]

#### 3.4.5 Other Analyses

In addition to the analysis above, subgroup analyses for vaccine virus transmission, shedding and stability would be performed by age group (<12 months,  $\geq$  12 months).

As exploratory analysis, probability of transmission of vaccine virus would be calculated for the pediatric participants using Greenwood / Reed-Frost models after each administration of study intervention. Further details are provided in [Appendix 2](#).

#### 3.4.6 Handling of Missing Data and Outliers

##### 3.4.6.1 Safety

In all participant listings, partial and missing data will be clearly indicated as missing. No search for outliers will be performed.

###### 3.4.6.1.1 Immediate

For unsolicited systemic AEs, a missing response to the “Immediate” field is assumed to have occurred after the 30-minute surveillance period and will not be imputed.

### **3.4.6.1.2 Causal Relationship**

By convention, all events reported at the administration site (either solicited or unsolicited) will be considered as related to the administered product and then referred to as reactions. In a same way, all solicited systemic events pre-listed in the eCRF are also considered as related to vaccination and will be considered as reactions.

For unsolicited systemic AE, missing relationship will be considered as related to study vaccine at the time of analysis.

The missing relationship to study procedures for SAEs will not be imputed.

### **3.4.6.1.3 Intensity**

For solicited reactions, missing intensities will be handled as described in [Section 4.2.4.1.1](#) For unsolicited AEs, missing intensities will remain missing and will not be imputed.

### **3.4.6.1.4 Start Date and End Date**

Missing or partially missing start dates or end dates for unsolicited AEs (including SAEs) will remain missing and not be imputed. If the start date is missing or partially missing, the time of onset will be considered to be missing. Nevertheless, unsolicited AEs with missing time of onset will be included in analyses according to the last vaccination (computed according to the [Section 4.2.4.2.3](#)). If either the start date or end date is missing or partially missing, the duration will be considered missing.

Missing or partially missing end dates for ongoing solicited AEs will remain missing and not be imputed.

### **3.4.6.1.5 Action Taken**

Missing actions taken will remain missing and will not be imputed.

## **3.4.6.2 Immunogenicity/viral shedding**

No imputation of missing values and no search for outliers will be performed. LLOQ and ULOQ management will be performed as described in [Section 4.2.6.1](#).

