9.3.2 Primary Endpoints

Vaccine virus transmission

Presence of vaccine virus detected by RSVt qRT-PCR in nasal swabs after the first study intervention administration (D01, D04, D08, D11, D15, D18, and D22) will be summarized in pediatric participants receiving placebo with 95% CIs:

- Number and percentage of participants with vaccine virus detected at each timepoint
- Number and percentage of participants with vaccine virus detected in at least one nasal swab

Vaccine virus shedding

Titer of vaccine virus shedding quantified by RSVt qRT-PCR in nasal swabs after each study intervention administration will be summarized at each timepoint (D01, D04, D08, D11, D15, D18, D22, D64, and D71) in pediatric participants by study intervention group with 95% CIs.

Vaccine virus stability

Presence of any vaccine virus mutation will be described in pediatric participants receiving placebo and ad-hoc close contact participants and may be described as well in a subset of pediatric participants receiving RSVt vaccine. Further details will be provided in the SAP.

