## 2 Objectives and Endpoints

**Table 2.1: Objectives and endpoints**

Objectives	Endpoints
Primary	

 
To describe the vaccine virus transmission in pediatric participants receiving placebo after the first study intervention administration
 
To describe the vaccine virus shedding in all pediatric participants with detected vaccine virus after each administration
 
To describe the vaccine virus stability in pediatric participants receiving placebo and ad-hoc close contact participants
 
	
 
Presence of vaccine virus in day (D)01, D04, D08, D11, D15, D18, and D22 nasal swabs, detected by quantitative reverse transcription polymerase chain reaction (RSVt qRT-PCR) Assay in pediatric participants receiving placebo
 
Titer of vaccine virus shedding in D01, D04, D08, D11, D15, D18, D22, D64, and D71 nasal swabs, quantified by RSVt qRT-PCR Assay in all pediatric participants
 
Difference in genetic sequence of mutated vaccine virus segments compared to the reference strain vaccine virus isolates in the vaccine virus positive swabs from pediatric participants receiving placebo and ad-hoc close contact participants
 

Secondary	
Immunogenicity	Immunogenicity

 
To evaluate the RSV A serum neutralizing and RSV serum anti-F immunoglobulin G (IgG) antibody responses to the study intervention after each study intervention administration in all pediatric participants
 
	
 
RSV A serum neutralizing antibody titers up to 28 days after the second administration (D01, D57, and D85)
 
RSV serum anti-F IgG Enzyme-linked Immuno-adsorbant Assay (ELISA) antibody titers up to 28 days after the second administration (D01, D57, and D85)
 

Safety	Safety

 
To assess the safety profile of the RSVt vaccine after each and any study intervention administration in pediatric participants.
 
	
 
Presence of any unsolicited systemic AEs reported in the 30 minutes after each study intervention administration
 
Presence of any solicited (ie, pre-listed in the participant's diary card [DC] and in the case
 

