### 3.3 Populations for Analyses

For the purposes of analysis, the following analysis sets are defined:

Participant Analysis Set	Description
Randomized	Pediatric participants for whom a study intervention group has been allocated.
Safety Analysis Set (SafAS)	Pediatric participants who have received at least one study intervention administration. All pediatric participants will have their safety analyzed after each vaccination according to the study intervention they actually received, and after any vaccination according to the study intervention received at the first study intervention administration.  Safety data recorded for a vaccine received out of the protocol design will be excluded from the analysis (and listed separately).
Full Analysis Set (FAS)	Subset of randomized pediatric participants who received at least one study intervention administration.  Pediatric participants will be analyzed according to the study intervention to which they were randomized.

Per-protocol analysis set (PPAS)	
The PPAS is a subset of the FAS.
 
The pediatric participants presenting with at least one of the following relevant protocol deviations will be excluded from the PPAS:
 

• Pediatric participant did not meet all protocol-specified inclusion criteria or met at least one of the protocol-specified exclusion criteria

• Pediatric participant did not receive first study intervention administration at D01

• Pediatric participant received a study intervention at D01 other than the one that he / she was randomized to receive

• Preparation and / or administration of study intervention at D01 not done as per-protocol

• Pediatric participant NOT having at least 4 nasal swabs (with a valid result) between D08 and D22, with a maximum of 5 days' time interval between 2 consecutive nasal swabs

• Pediatric participant received a protocol-prohibited therapy before collection of nasal swab between D08 and D22

• Pediatric participant with an emergency unblinding performed by the investigator before collection of nasal swab at D22

• Pediatric participant who was RSV- exposed before study intervention administration at D01

Other analysis set	An analysis set will be used to document transmission of vaccine virus in the ad-hoc close contact participants

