**Table 3.1: Descriptive statistics produced**

Disposition and follow-up description	Categorical data	Number of participants. Percentage of participants.
	Continuous data	Mean, standard deviation, quartiles, minimum, and maximum.
Baseline characteristics	Categorical data	Number of participants. Percentage of participants.
	Continuous data	Mean, standard deviation, quartiles, minimum and maximum.
Clinical safety results	Categorical data	Solicited: Number and percentage (95% CIs) of participants. Unsolicited: Number and percentage (95% CIs) of participants and number of events.
Vaccine virus shedding results	Categorical data	Number and percentage (95% CIs) of participants.
	Continuous data	Mean and standard deviation, quartiles, minimum, and maximum.
Transmissibility results	Categorical data	Number and percentage (95% CIs) of participants.
Vaccine virus stability	Categorical data	Number and percentage (95% CIs) of participants.
Immunogenicity results	Categorical data (cutoff)	Number and percentage (95% CIs) of participants.
	Continuous data (titer / data)	Log10: Mean and standard deviation. Anti-Log10 (work on Log10 distribution, and anti-Log10 applied): Geometric mean, 95% CI of the geometric mean, quartiles, minimum, and maximum. Graphical representation by Reverse Cumulative Distribution Curve (RCDC)
Infectivity results	Categorical data	Number and percentage (95% CIs) of participants.
RSV WT infection	Categorical data	Number and percentage (95% CIs) of participants, number of events, and 95% CI.

The statistical methodology will be based on the use of two-sided 95% confidence intervals (CI).

All endpoints will be summarized by study intervention group. For the main parameters, 95% CI of point estimates will be calculated using the normal approximation for quantitative data and using the exact binomial distribution (Clopper-Pearson method) for proportions.

For immunogenicity data, assuming that Log10 transformation of the titers/titers ratio follows a normal distribution, at first, the mean and the 95% CI will be calculated on Log10 (titers/titers ratio) using the usual calculation for normal distribution (using Student's t distribution with n-1 degree of freedom), then antilog transformations will be applied to the results of calculations, in

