#### 3.4.2.2 Vaccine virus shedding

Titer of vaccine virus shedding evaluated by RSVt qRT-PCR in nasal swabs after each vaccination will be summarized at each timepoint (D01, D04, D08, D11, D15, D18, D22, D64, and D71) in pediatric participants by study intervention group with 95% CIs:

- Number and percentage of participants with detected shedding ( $\geq$ LOD) at each timepoint
- Number and percentage of participants with quantified shedding ( $\geq$ LLOQ) at each timepoint

In addition, titer of vaccine virus shedding will be summarized using descriptive statistics as presented in [Table 3.1](#).

Viral shedding analyses will be performed on the SafAS.

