## 4.2.6 Immunogenicity

### 4.2.6.1 Computed Values for Analysis

In order to appropriately manage extreme values (< lower limit of quantification [LLOQ] and  $\geq$  upper limit of quantification [ULOQ]) for analysis purposes, the following computational rule is applied to the values provided in the clinical database for each blood sample drawn:

- If a value is < LLOQ, then use the computed value LLOQ/2
- If a value is between  $\geq$  LLOQ and < ULOQ, then use the value
- If a value is  $\geq$  ULOQ, then use the computed value ULOQ

For the RSV serum anti-F IgA antibodies, we will consider the LOD value for the calculation instead of the LLOQ.

Note for titers converted into IU/mL:

The IU/mL is computed using the following calibration formulae:

$$\text{IU/mL} = \frac{\text{Sample Titer}}{(\text{Assay calibrator})/\text{Assigned Potency}} = \frac{\text{Sample Titer}}{(\text{Assay calibrator})/\text{Assigned Potency}}$$

Where:

- *Sample Titer*: This is the titer directly observed from the sample using one plate.
- *Assigned Potency*: The established internal reference standard and replacement for International
- *Assay calibrator*: Each plate will also measure the titer of the reference standard

Because of this calibration formula, LLOQ related to titers can be calibrated to different IU/mL depending on the observed titer of calibrator (international reference or in-house reference); so titer < LLOQ is not consistent converting to IU/mL from run to run.

As a consequence, for any value reported as “< X”, we use the computed value X/2. No ULOQ is defined.

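### No planned titer summary matches the primary shedding objective: titers are summarized over all dosed children in each arm, with one substitution value for undetected and unquantifiable swabs and no stated log10 scale

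*SAP*

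**What the plan says.** The second primary objective in SAP Table 2.1 is "To describe the vaccine virus shedding in all pediatric participants with detected vaccine virus after each administration". The endpoint beside it is the titer "quantified by RSVt qRT-PCR Assay in all pediatric participants", with no condition on detection. SAP 3.4.2.2 states "Viral shedding analyses will be performed on the SafAS", and SAP 3.3 defines that set as "Pediatric participants who have received at least one study intervention administration". Results are given by study intervention group and by visit.

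SAP 3.4.2.2 plans the number and percentage of children with detected shedding (at or above LOD) and with quantified shedding (at or above LLOQ), plus titer statistics from Table 3.1. For continuous shedding data that table lists "Mean and standard deviation, quartiles, minimum, and maximum". It names log10 and geometric means in the immunogenicity rows only.

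SAP 3.4.6.2 covers immunogenicity and viral shedding together: "LLOQ and ULOQ management will be performed as described in" Section 4.2.6.1. There, for a value below LLOQ, the instruction is "then use the computed value LLOQ/2". The rule is worded for blood samples, and its only LOD variant is for serum anti-F IgA.

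Protocol 9.3.2 says "Titer of vaccine virus shedding quantified by RSVt qRT-PCR in nasal swabs after each study intervention administration will be summarized at each timepoint", by group with 95% CIs. Table 3.1 lists no CI for continuous shedding data.

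**The concern.** The objective asks how much virus the shedding children shed. The planned titer statistics combine shedders and non-shedders within an arm, so they answer a different question and move with the share of negative swabs. The substitution rule adds to this. The SAP separates detected from quantified shedding when it counts children, then drops the distinction when it assigns titers.

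Titer is a primary endpoint. SAP 3.5 sends shedding data to Health Authorities at the interim, before Phase III. Protocol 4.2 links the level of shedding in vaccinees to the probability of transmission. A titer figure that mainly reflects how many children were negative would be a poor basis for either use. The study tests no hypotheses, so the description is itself the deliverable.

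**Working it through.** **Tracing the text.** The plan gives no titer figure to reproduce, so the first check is to follow the rules.

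1. Target of the objective: children with detected virus. Target of the endpoint and analysis set: all dosed children, by arm. These differ, and no titer summary among virus-positive children is specified.
2. Swab below LOD: it is also below LLOQ, so it becomes LLOQ/2. Swab from LOD to below LLOQ: also LLOQ/2. The two states get one value.
3. Scale: log10 is stated for immunogenicity only. The qRT-PCR assay description is not visible, so the scale on which titers are reported is unknown.

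**Size.** From the documents: 50 children per arm. Assumed, because the documents give no values: 30% positive at a visit (15 of 50), shedders' log10 titer with mean 5 and SD 1, LLOQ between 10^2 and 10^3, and every negative swab set to LLOQ/2. The two scales are alternatives, and only one can apply.

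*If titers are analysed on log10:*

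- Arm mean log10 = 0.3 × 5 + 0.7 × (log10 LLOQ − 0.301).
- LLOQ 10^2: 1.5 + 0.7 × 1.699 = 2.689, a geometric mean of about 490.
- LLOQ 10^3: 1.5 + 0.7 × 2.699 = 3.389, a geometric mean of about 2,450.
- Shedders: 10^5 = 100,000. The arm figure is lower by a factor of about 205 or 41.

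*If titers are analysed raw:*

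- Shedders' arithmetic mean = 10^5 × exp((ln 10)²/2) ≈ 1,417,000.
- Contribution of shedders to the arm mean = 0.3 × 1,417,000 ≈ 425,000.
- Contribution of LLOQ/2 = 0.7 × 50 = 35, or 0.7 × 500 = 350. That is 0.008% or 0.08% of the mean, so the substituted value hardly matters here.
- Dilution = 1/0.3 ≈ 3.3-fold, from the positive share alone.
- Normal-approximation 95% CI (mean ± 1.96 × SD/√50, LLOQ 10^2, 20,000 simulated trials): the lower limit is negative in about 62% and the interval covers the true mean in about 50%. With 60% positive the figures are about 40% and 56%.
- The same raw-scale CI among shedders only: the lower limit is negative in about 53% (30% positive) or 38% (60% positive). Restriction to shedders does not cure the skew.

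*On either scale:* with fewer than half of the swabs positive, the arm median is LLOQ/2 (or its log10) and carries no titer information. At 30% positive, 35 of 50 values are LLOQ/2, so the lower quartile is LLOQ/2 as well.

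**The case against.** Four points on the other side are fair.

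- The analysis follows the stated endpoint, which covers all pediatric participants. That is correct. The fault is the mismatch between objective and endpoint, and the analysis inherits it.
- The percentages at or above LOD and LLOQ already separate undetected, detected and quantified swabs at every visit, and the quartiles and maximum say something about the upper tail. This stands, and it limits the defect to the titer summary. It does not supply a typical titer among shedders.
- The LLOQ/2 rule is written for blood samples and reaches swabs only by cross-reference, and the SAP does not say how an undetected swab is recorded. This also stands. But no other swab rule is visible, and if this one was not meant to apply, undetected swabs have no rule.
- The study is descriptive, with no decision rule based on titers, and the transmission endpoint is unaffected. This bears on severity.

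Several stronger readings are tempting but not supported.

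- A reader might infer that placebo and vaccine children are averaged together. They are not; results are by arm.
- A reader might add the 41- to 205-fold shortfall to the negative confidence limits. The first arises on log10 and the second on the raw scale.
- A reader might say that the raw-scale mean is driven by the assay limit. In the example LLOQ/2 supplies under 0.1% of it.
- A reader might take it as settled that titers are untransformed. The assay text is missing, and results may already be in log10 units.
- A reader might take a raw-scale titer CI as firmly planned. Protocol 9.3.2 and the general rule in SAP 3.4.1 point to a CI. In SAP 3.4.2.2 the CIs introduce the two percentages, and Table 3.1 lists none for continuous shedding data.

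**Conclusion.** The concern holds for the titer summary. As written, no planned titer statistic describes shedding in children with detected virus, the visible rule gives undetected and unquantifiable swabs the same titer, and the scale and CI for titers are not settled.

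The textual points rest on the documents alone. The sizes rest on assumed assay values and on the scale. On log10, the arm geometric mean would be about 490 to 2,450 against 100,000 in shedders. On the raw scale, the mean would be about 3.3-fold diluted, with an interval that covers about half the time. Other positive shares, titer levels or LLOQs would change these figures.

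This should be fixed before the titer tables are produced. It does not undermine the percentages of children shedding or the transmission endpoint.

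**What to change.** 1. Reconcile the objective and the endpoint, so that the population for the titer summary is stated once.
2. Keep the percentages at or above LOD and at or above LLOQ on the full safety analysis set.
3. Add, by arm and visit, a titer summary among swabs at or above LOD, on log10: geometric mean, t-based 95% CI, and n.
4. Write a swab rule separate from the serology rule: LLOQ/2 only for swabs from LOD to below LLOQ, and no titer for swabs below LOD.
5. State the scale on which qRT-PCR titers are reported, and bring Table 3.1 into line with Protocol 9.3.2 on the CI.
6. Keep any titer summary over all dosed children as supportive.

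Restriction to shedders and the log10 scale are both needed; neither is enough alone. Tables by baseline serostatus or of peak titer per shedder may be useful, but they answer no defect shown here and are not part of the fix.

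The change costs SAP wording and table shells, with no new data. The price is a smaller n per cell. With 15 shedders and SD 1 log10, the half-width is 2.145 × 1/√15 = 0.554 log10, so the CI runs from the geometric mean divided by about 3.6 to the geometric mean multiplied by about 3.6. Cells with very few positive swabs are better listed individually.

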## **3.4.6.3 Efficacy**

No efficacy.

### 3.5 Interim Analyses

- An unblinded interim analysis will be performed on available data collected from D01 (V01) to D22 (V07) for participants randomized on or before 21July2023, in two steps:
  - The first step will be performed on available shedding / transmission data by RSVt qRT-PCR assay up to 21 days after the first study intervention administration, that will also include baseline immunogenicity data, safety data up to 21 days after the first study intervention administration, in order to share preliminary data to Health Authorities before moving to phase III clinical development. Randomization code will be broken for the Sponsor but blinding will be maintained at sites and participants/parents levels. Some listings will be generated to define the next steps for nasal swab testing (sequencing, plaque assay and WT RT-PCR).
  - The second step will be performed when subsequent data up to 21 days after the first study intervention administration will be available (e.g. segment sequencing, plaque assay and WT RT-PCR data).
- An additional unblinded interim analysis will be performed once all data collected from D01 (V01) to D22 (V07) from all participants is available. A two-step process of analysis will also be applied.
- The final unblinded statistical analysis will address the objectives on all participants  
No statistical adjustment is necessary because no hypotheses will be tested.  
This study will not include an early safety data review.

### 3.6 Data Monitoring Committee (DMC)

No DMC will be established.

## 4 Complementary Information on Assessment Methods

Study assessments and procedures are detailed in Section 8 of the protocol. This section focusses on complementary/additional information not detailed in the protocol.

### 4.1 Complementary Information for Endpoints Assessment Methods

#### 4.1.1 Primary Endpoints and Assessment Methods

##### 4.1.1.1 Transmission

See section 8.1.2 and section 9.3.2 of the protocol

##### 4.1.1.2 Vaccine virus shedding

See section 8.1.2 and section 9.3.2 of the protocol

##### 4.1.1.3 Stability

See section 8.1.2 and section 9.3.2 of the protocol

#### 4.1.2 Secondary Endpoints and Assessment Methods

##### 4.1.2.1 Immunogenicity

See section 8.1.3 and section 9.3.3 of the protocol

